### **5.2.6 Safety Endpoint: Electrocardiogram (ECG)**

12-lead ECGs will be recorded in triplicate at the scheduled time points (at least 2 minutes apart per time point). Each ECG tracing will be taken 5 minutes apart. ECGs will be read at the site for clinical decision making and transmitted to a central reviewer. Data from the central reviewer will be used in summary presentations.

The routine 12-lead ECG results will be summarized by dose level and by time point.

Interpretations of routine 12-lead ECG results will be summarized by dose level and by time point.

12-lead ECG data interpretations and quantitative values will be listed.

### **5.2.7 Safety Endpoint: Eastern Cooperative Oncology Group Performance Status (ECOG PS)**

The ECOG Scale [Oken et al., 1982] will be used to assess performance status at time points outlined in the Protocol in the Schedule of Assessments.

### **5.3 Pharmacokinetic Variables**

Cellular DNA load and kinetic parameter estimates of ASP0739 will be evaluated for each cohort as outlined in the Protocol in the Schedule of Assessments.

Cellular DNA load and kinetic parameters for ASP0739 pharmacokinetics will be summarized by using descriptive statistics including n, mean, standard deviation, minimum, median, maximum, coefficient of variation (CV), geometric mean, and geometric CV.

Time-course of cellular DNA load will be plotted as appropriate. Participants with sufficient cellular DNA samples will have kinetic parameter estimates for ASP0739 including calculation of AUC (including  $AUC_{last}$ ,  $AUC_{28d}$ ,  $AUC_{inf}$ ,  $C_{max}$ ,  $C_{trough}$  and  $t_{max}$ ) using standard noncompartmental analysis. For pharmacokinetic parameters,  $t_{max}$ , n, median, minimum and maximum will be calculated.

### **5.4 Pharmacodynamic Variables**

Pharmacodynamic effects of ASP0739 as monotherapy will be assessed with immune cell populations (NKT cells, Treg cells, etc.).

### **5.5 Other Variables**

- Duration of exposure (days)
  - Duration of exposure to a study drug will be calculated in days, using the following formula:  
$$(Last\ date\ of\ exposure - date\ of\ first\ dose) + 1;$$
 where last date of exposure= initial infusion date of the last cycle + 27 or death date if death occurs within last cycle.
    - When the start or stop date is missing, then the exposure will be treated as missing.
  - (Last date of exposure – date of first dose) + 1; where last date of exposure= initial infusion date of the last cycle + 27 or death date if death occurs within last cycle.
    - When the start or stop date is missing, then the exposure will be treated as missing.
- Cumulative actual dose (# of cells)
  - Total amount of IP administered to the participant from first dose date to last dose date
- Number of cycles initiated
  - Total number of cycles with non-zero dosing in the cycle
- Planned dose intensity
  - Planned dose/planned number of cycles
- Actual dose intensity
  - Defined as the cumulative actual dose divided by number of cycles
- Relative dose intensity (RDI; %)
  - $$\frac{\text{Actual Dose Intensity}}{\text{Planned Dose Intensity}} \times 100$$

## **6 STATISTICAL METHODOLOGY**

### **6.1 General Considerations**

For continuous variables, descriptive statistics will include the number of participants (n), mean, standard deviation, median, minimum, and maximum. When needed, the use of other percentiles (e.g., 10%, 25%, 75% and 90%) will be reported in the relevant section. In addition, for plasma concentrations and continuous PK parameters, the coefficient of variation (CV) and the geometric mean will also be calculated. Frequencies and percentages will be displayed for categorical data. Percentages by categories will be based on the number of participants with no missing data, i.e., will add up to 100%.

Summaries based on FAS and RAS (e.g., disposition, baseline, and efficacy data) will be presented by planned treatment, unless specifically stated otherwise. Safety analysis and other summaries based on SAF, PKAS or PDAS will be presented by actual dose level received.

Baseline is defined as the last available measurement prior to the first dose of IP.

Unless otherwise specified, all summaries will be presented overall, by dose level, and by phase.

All data processing, summarization, and analyses will be performed using Statistical Analysis Software (SAS)® Version 9.4 or higher on Linux. Specifications for table, figure, and listing (TLF) formats can be found in the TLF specifications for this study.

Study day will be calculated in reference to the first dose date. For assessments conducted before the first dose, study day will be calculated as (assessment date – first dose date). For assessments conducted on or after the first dose, study day will be calculated as (assessment date – first dose date + 1).

For the definition of subgroups of interest, please refer to Section [6.8](#).

### **6.2 Study Population**

#### **6.2.1 Disposition of Participants**

The following participant data will be presented:

- Number and percentage of participants with informed consent, discontinued before allocation to treatment, allocated to treatment (overall only)
- Number and percentage of participants allocated to treatment in each analysis set, by dose level, phase, and overall
- Number and percentage of participants completed and discontinued treatment, by primary reason for treatment discontinuation for SAF, by dose level, phase, and overall
- Number and percentage of participants completed and discontinued the study at 30-, 60-, and 90-day follow-up, by primary reason for post-study period discontinuation for SAF by dose level, phase, and overall

- Number and percentage of participants completed and discontinued the study during the observation period, by primary reason for post-study period discontinuation for SAF by dose level, phase, and overall
- Number and percentage of participants completed and discontinued the study during the observation period, by primary reason for post-study period discontinuation for SAF by dose level, phase, and overall

All disposition details and dates of first and last evaluations for each participant will be listed.

### **6.2.2 Protocol Deviations**

Protocol deviations as defined in the study protocol (Section 8.1.6 Protocol Deviations) will be assessed for all participant enrolled. The number and percentage of participants meeting any criteria will be summarized for each criterion and overall, by dose level, phase, and overall as well as by study site. Participants deviating from a criterion more than once will be counted once for the corresponding criterion. Any participants who have more than one protocol deviation will be counted once in the overall summary. A data listing will be provided by site and participant.

The protocol deviation criteria will be uniquely identified in the summary table and listing. The unique identifiers will be as follows:

PD1 - Entered into the study even though they did not satisfy entry criteria,

PD2 - Developed withdrawal criteria during the study and was not withdrawn,

PD3 - Received wrong treatment or incorrect dose,

PD4 - Received excluded concomitant treatment.

PD5 - Clinical study procedure conducted prior to subject signing informed consent.

PD6 - Event not reported within the expected turn-around time per protocol reporting requirements.

PD7 - Missed safety or efficacy assessments related to primary or key secondary endpoints.

### **6.2.3 Demographic and Other Baseline Characteristics**

Demographics and baseline characteristics will be summarized with descriptive statistics.

Number and percentage of participants allocated to treatment in each country and site will be presented by dose level, phase, and overall for SAF.

Descriptive statistics for age, weight, body surface area (BSA), and height at study entry will be presented. Frequency tabulations for sex, ethnicity, age group (defined in Section 6.8), race, region, and baseline ECOG will be presented. This will be done for SAF and RAS, by dose level, phase, and overall.

Medical history and conditions existing at baseline will be coded in MedDRA and summarized by System Organ Class (SOC) and Preferred Term (PT) as well as by PT alone, by treatment group and overall for the SAF. Baseline conditions are defined as those ongoing

at the time of informed consent or arise following the time of informed consent and before the first dose of IP. For ongoing medical conditions, Common Terminology Criteria for Adverse Events (CTCAE) grade will be provided in listing.

#### **6.2.4 Disease History**

Frequency tabulations will be presented for disease history including tumor subtype and prior anti-cancer therapies.

#### **6.2.5 Previous and Concomitant Medications**

Previous medications include medications taken within 28 days prior to cycle 1 day 1 and all anticancer treatment received 28 days prior to IP administration. Previous medications are coded with World Health Organization Drug Dictionary (WHO-DD), and will be summarized in descending percentage order by Preferred WHO Name (Ingredients), as well as by therapeutic subgroup (ATC 2nd level) and chemical subgroup (ATC 4th level) and preferred WHO name by dose level, phase, and overall for the SAF.

Concomitant medications include medications taken after the first dose of study drug up until the 90 days follow-up visit. As with previous medication, concomitant medication will be summarized by dose level, phase, and overall by therapeutic subgroup (ATC 2nd level) and chemical subgroup (ATC 4th level) and preferred WHO name for the SAF. Participants taking the same medication multiple times will be counted once per medication and investigational period. A medication which can be classified into several chemical and/or therapeutic subgroups is presented in all chemical and therapeutic subgroups.

#### **6.2.6 Prior Radiation Therapy**

Frequency tabulations of participants with prior radiation therapy will be presented for SAF.

#### **6.2.7 New and Prior Anti-Cancer Therapy**

Frequency tabulations of participants with prior and with new anti-cancer therapy will be presented for SAF.

### **6.3 Study Drug**

#### **6.3.1 Exposure**

The following information on drug exposure will be presented with descriptive statistics (n, mean, standard deviation, median, minimum, maximum) for the SAF:

- Duration of exposure (days)
- Cumulative actual dose (# of cells)
- Number of cycles initiated
- Planned dose intensity
- Actual dose intensity
- Relative dose intensity (RDI; %); in addition to descriptive statistics, frequency tabulations will be presented for RDI for the following categories:
  - <50%
  - 50% to <=80%

- >80%
- Unknown
- Number and percentage of participants with dose adjustments or interruptions will be presented for the SAF.

## **6.4 Analysis of Efficacy**

Efficacy analysis will be conducted on the FAS and RAS (RAS for response-related analyses, FAS for survival and other time-to-event analyses). Best overall responses are summarized based on iRECIST and RECIST 1.1. Efficacy analyses will be summarized by dose level, phase, and overall. Swimmer plots will be produced displaying participants' overall disease response experience, spider plots to display percent change in tumor size, and waterfall plots to display maximum tumor shrinkage rate.

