9.4.1 General Considerations

In general, data will be summarized with descriptive statistics for continuous endpoints, and frequency and percentage for categorical endpoints, unless otherwise specified. Percentages by categories will be based on the number of participants with no missing data (i.e., will add up to 100%).

Baseline will be defined as the last nonmissing observation prior to the first administration of IP, unless otherwise specified.

In general, dose escalation and safety lead-in data will be summarized by dose level. Phase 2 data will be summarized by monotherapy and combination therapy arms and by tumor types, unless specified otherwise.

Demographics and baseline characteristics will be summarized for all treated participants.

The number and percentage of participants who completed and discontinued treatment and reasons for treatment discontinuation will be presented for all enrolled participants, for participants in the safety analysis set (SAF). Similar tables for screening disposition, follow-up period disposition and survival follow-up disposition will also be presented for all treated participants. All disposition details and dates of first and last evaluations for each participant will be listed.

Previous and concomitant treatment and medical history will be listed. IP exposure will be summarized using descriptive statistics and will be listed.

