9.4.2.1 Analysis of Primary Endpoint

9.4.2.1.1 Primary Analysis

iORR is defined as the proportion of participants for each dose level whose best overall response is rated as confirmed iCR or iPR per iRECIST by independent central review. iORR for each dose level will be calculated and its 95% confidence interval will be constructed by Clopper-Pearson method.

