### ASP0739 Combination with Pembrolizumab:

A total of approximately 158 participants may be enrolled in combination therapy.

*Combination Therapy Safety Lead-in:*

The sample size of approximately 6 to 9 participants for safety lead-in is not based on a statistical power calculation. The number of participants enrolled will be dependent on the DLT incidence. The estimated number of participants should provide adequate information for the safety objectives of the study.

*Phase 2 Combination Therapy:*

It is estimated that up to approximately 149 participants may be enrolled in the combination therapy arms. The iORR is monitored using the BOP2 design.

For each indication, with assumptions mentioned in the statistical hypotheses section below, the statistical power would be approximately at least 0.80 while controlling the type I error rate at 0.05 (1-sided).

Statistical Hypotheses:

*Phase 2 Single Agent (SS, MRCL, Ovarian):*

H0: iORR is 10%, at which the treatment is deemed as unacceptable.

H1: iORR is at least 25%, at which the treatment is deemed as acceptable.

*Solid tumors known to express NY-ESO-1 (melanoma, NSCLC-adenocarcinoma and squamous cell as well as ESSC):*

There is no formal statistical hypothesis for this cohort.

*Phase 2 Combination Therapy:*

*SS:*

H0: iORR is 20%, at which the treatment is deemed as unacceptable.

H1: iORR is at least 35%, at which the treatment is deemed as acceptable.

*MRCL:*

H0: iORR is 20%, at which the treatment is deemed as unacceptable.

H1: iORR is at least 35%, at which the treatment is deemed as acceptable.

*Ovarian:*

H0: iORR is 5%, at which the treatment is deemed as unacceptable.

H1: iORR is at least 20%, at which the treatment is deemed as acceptable.

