### **6.4.1 Analysis of Primary Efficacy Endpoint**

#### **6.4.1.1 Analysis of Primary Efficacy Endpoint: Objective Response Rate per iRECIST (iORR)**

iORR for each dose level will be calculated and its 95% confidence interval will be constructed by Clopper-Pearson method for the endpoints of:

- iORR with confirmed response by investigator assessment
- iORR with unconfirmed response by investigator assessment

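### The SAP's response summaries have no tumor-type split for phase 2, although the hypotheses and decision rules it keeps are per indication

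*SAP*

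**What the plan says.** **Strata in the SAP.** The general rule in SAP 6.1 is: "Unless otherwise specified, all summaries will be presented overall, by dose level, and by phase". SAP 6.4 repeats it for efficacy: "Efficacy analyses will be summarized by dose level, phase, and overall". For the primary endpoint, SAP 6.4.1.1 says "iORR for each dose level will be calculated", with an exact 95% interval; SAP 6.4.2.1 does the same for ORR. SAP 6.4.2.2 and 6.4.2.3 give iDCR and DCR for each group, without defining the group. OS, iPFS, PFS, iDOR and DOR are listed only (SAP 6.4.2.4 to 6.4.2.8).

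**Tumor type in the SAP.** It appears in the design description, in the hypotheses, and as a disease-history tabulation (SAP 6.2.4). SAP 6.1 refers to Section 6.8 for subgroups of interest, but 6.8 defines none.

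**Protocol.** Section 9.4.1 says: "Phase 2 data will be summarized by monotherapy and combination therapy arms and by tumor types, unless specified otherwise". Section 9.4.2.1.1 nevertheless words the primary analysis as "iORR for each dose level will be calculated and its 95% confidence interval will be constructed by Clopper-Pearson method".

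**Hypotheses and rules.** SAP Section 3 states the single-agent null for synovial sarcoma (SS), myxoid/round cell liposarcoma (MRCL) and ovarian cancer as "H0: iORR is 10%, at which the treatment is deemed as unacceptable", and claims power and type I error for each indication. SAP 2.2 keeps the 18-then-43 rule for each tumor-specific cohort. The melanoma/NSCLC/ESCC cohort has no formal hypothesis.

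**Termination.** SAP Section 1 says that the study ended early and that the SAP covers only part of the protocol analysis. There is no central review and no combination treatment.

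**The concern.** The SAP keeps indication-specific questions but plans no table that gives an indication-specific response rate. Phase 2 cohorts open at the recommended phase 2 dose, and SAP 6.1 presents FAS and RAS summaries by planned treatment. Dose level within phase 2 therefore does not separate the tumor types. The phase 2 row would be one rate over SS, MRCL, ovarian and the melanoma/NSCLC/ESCC cohort, as far as each was enrolled. A dose-level row not split by phase, and the overall row, could also mix in phase 1 participants with other tumors.

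The value of such a rate depends on the tumor mix enrolled, and it corresponds to no stated null or alternative. If one tumor type responded and the others did not, the tabulated rate would not show it.

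**Working it through.** **1. The unit the plan's own figures refer to.** Inputs for the single-agent rule, from SAP 2.2 and 3 and the boundary table in Protocol 4.1: stage 1 n1 = 18, stop at 2 or fewer responses; total n = 43, effective at 8 or more; null 10%, alternative 25%. The stated characteristics are power of about at least 0.80 and one-sided type I error of 0.05, for each indication.

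Probability of declaring activity at true rate p:

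sum over x1 = 3 to 18 of Bin(x1; 18, p) × P(X2 ≥ 8 − x1), with X2 ~ Bin(25, p)

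- p = 0.10: 0.0480
- p = 0.25: 0.8003

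The stated figures reproduce for one tumor type at a time. The combination rules do too: SS and MRCL (22, stop at 3 or fewer; 60, 18 or more; 20% against 35%) give 0.0417 and 0.8204; ovarian (10, stop at 0; 29, 4 or more; 5% against 20%) gives 0.0468 and 0.8011. The design is consistent, and all of it is per indication.

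**2. The unit the SAP tables use.**

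| Item | Unit |
|---|---|
| Hypotheses, power, type I error (SAP 3) | indication |
| Decision rules (SAP 2.2) | tumor-specific cohort |
| Default phase 2 summary (Protocol 9.4.1) | arm and tumor type, unless specified otherwise |
| iORR wording (Protocol 9.4.2.1.1) | dose level |
| Efficacy summaries (SAP 6.1, 6.4) | dose level, phase, overall |

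The last row has no tumor type. An estimate matching the 8-of-43 rule is a per-tumor one: at the boundary, 8/43 = 18.6% (Clopper-Pearson 95% CI 8.4% to 33.4%).

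**3. What pooling could do: illustration only.** Assume true rates of 25% in one indication and 10% in the other two. These are not in the documents and are not a forecast.

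- Equal cohorts: (0.25 + 0.10 + 0.10)/3 = 0.15.
- At 43 each, expected responders are 43 × 0.25 = 10.75, about 11, and 43 × 0.10 = 4.3, about 4, in each of the others.
- By tumor type: 11/43 = 25.6% (13.5% to 41.2%) and 4/43 = 9.3% (2.6% to 22.1%), twice.
- Pooled: 19/129 = 14.7% (9.1% to 22.0%).
- With the 40-participant cohort in the same row, at an assumed 0% to 10%: (43 × 0.45 + 0)/169 = 11.4% to (43 × 0.45 + 4)/169 = 13.8%.

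**4. What is known about the actual size.** The only count in the documents is in Protocol 2.3.1.1: 4 participants as of 06 May 2022, all in dose escalation. No phase 2 count is given.

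**The case against.** The strongest reply is that the SAP follows the protocol. The tumor-type sentence in Protocol 9.4.1 is a default with an exception clause, and the protocol's own efficacy sections word iORR and most of the other endpoints by dose level. SAP 6.4.1.1 repeats that wording almost unchanged. This stands: a reader might infer that the SAP breaches a protocol requirement, and the documents do not support that. The loose wording starts in the protocol. It does not settle the matter, though, because Protocol 9.1 frames the hypotheses by indication and dose level together, and wording by dose level does not expressly remove tumor type.

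A second reply is that little is lost. The primary endpoint and the monitoring rule rest on confirmed response by central review, which will not exist. There are no combination data, and SAP 6.4 plans estimates with intervals, not tests. This also stands: a tumor-type row would not restore the planned comparison, and it would be wrong to infer that pooling costs the trial a hypothesis test.

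Third, phase 2 may hold few or no participants. At 0 of 2 the exact interval runs from 0% to 1 − √0.025 = 84%, so per-tumor rates would say little, and participant-level displays would be more useful. The SAP plans swimmer, spider and waterfall plots and data listings, and leaves layouts to table specifications that are not among the documents. Those may show tumor type, but the SAP does not require it.

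Early termination does not explain the omission. SAP Section 1 and the notes to the objectives table name what was dropped, and tumor-type reporting is not among the items. The SAP does not say that phase 2 was unopened, and it keeps phase as a stratum.

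**Conclusion.** The point holds as a reporting gap. Followed as written, the SAP gives a phase 2 response rate that matches none of the indication-specific hypotheses or rules it retains. Sample size, power and type I error are unaffected.

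The size cannot be stated. It depends on how many phase 2 participants were treated and in which tumor types, which the documents do not give; it may be nil. A reader might infer from the 15% example that an active tumor type will be masked in this trial. The documents do not support that: the rates and cohort sizes are assumed, and the only documented participants are 4 in dose escalation. The case for acting rests on the low cost and on the SAP's internal inconsistency, not on a demonstrated loss.

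**What to change.** - In SAP 6.4 and 6.4.1 to 6.4.2, add that phase 2 response is also summarized by tumor type.
- Identify tumor type on the swimmer, spider and waterfall plots and in the OS, iPFS, PFS, iDOR and DOR listings, which are the only planned output for those endpoints.
- Label any rate pooled over tumor types as descriptive.
- If phase 2 was never opened, say so in SAP Section 1 and delete the phase stratum, keeping tumor type on the plots and listings.

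The cost is one by-variable in tables already planned, or one sentence and a deletion. No new data or change to the design is needed.

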### **6.4.1 Analysis of Primary Efficacy Endpoint**

#### **6.4.1.1 Analysis of Primary Efficacy Endpoint: Objective Response Rate per iRECIST (iORR)**

iORR for each dose level will be calculated and its 95% confidence interval will be constructed by Clopper-Pearson method for the endpoints of:

- iORR with confirmed response by investigator assessment
- iORR with unconfirmed response by investigator assessment

### **6.4.2 Analysis of Secondary Efficacy Endpoints**

#### **6.4.2.1 Analysis of Secondary Efficacy Endpoint: Objective Response Rate per RECIST v1.1 (ORR)**

ORR for each dose level will be calculated and its 95% confidence interval will be constructed by Clopper-Pearson method for the endpoints of:

- ORR with confirmed response by investigator assessment
- ORR with unconfirmed response by investigator assessment

